### **5.7.3 Data Collection and Follow-up for Withdrawn Subjects**

Intervention is a one-time injection. Therefore, patients who opt out of the study will not be able to opt out of treatment once injection is performed.

## **6 Study Agent**

### **6.1 Description and Formulation**

Botox will be prepared by the central pharmacy per standardized protocol as directed by Allergan:

Prior to injection, reconstitute each vacuum-dried vial of BOTOX with only sterile, preservative-free 0.9% Sodium Chloride Injection USP. Draw up the proper amount of diluent (1 mL) in the appropriate size syringe, and slowly inject the diluent into the vial. Discard the vial if a vacuum does not pull the diluent into the vial. Gently mix BOTOX with the saline by rotating the vial. Record the date and time of reconstitution on the space on the label. BOTOX should be administered within 24 hours after reconstitution. During this time period, reconstituted BOTOX should be stored in a refrigerator (2° to 8°C).

**NOTE:** State is the study agent is IND/IDE exempt. If not, state reference number and identify the holder.

### **6.2 Packaging**

- Study drug will be supplied by the central pharmacy within 24 hours of scheduled injection per their usual protocol.
- Drug will be packaged in a clear plastic bag with the patient's identifying information clearly visible on the outside and placed in the refrigerator set between 2° and 8° C.

- Individual syringes will also be labeled with subject's identifying information

### **6.3 Preparation, Administration and Storage of Study Drug**

Botox will be prepared by and delivered by the UW Pharmaceutical Research Center (PRC) per standardized protocol as directed by Allergan:

Prior to injection, reconstitute each vacuum-dried vial of BOTOX with only sterile, preservative-free 0.9% Sodium Chloride Injection USP. Draw up the proper amount of diluent (1 mL) in the appropriate size syringe, and slowly inject the diluent into the vial. Discard the vial if a vacuum does not pull the diluent into the vial. Gently mix BOTOX with the saline by rotating the vial. Record the date and time of reconstitution on the space on the label. BOTOX should be administered within 24 hours after reconstitution. During this time period, reconstituted BOTOX should be stored in a refrigerator (2° to 8°C).

Contact agent at the UW Pharmaceutical Research Center is [name], who can be reached at [contact].

### **6.4 Route of Administration**

- Dose will be determined based upon patient location of symptoms as follows:
  - - 50 units total (25 proximal and 25 distal) into the TA for anterior symptoms
  - - 50 units in to the peroneal longus for the lateral compartment
  - - 50 units into each the medial and lateral gastrocnemius for superficial posterior symptoms
  - - 50 units into the tibialis posterior for deep posterior symptoms
- Treatment duration: Established duration of action on muscular weakness of other uses of Botox is between 2 and 4 months. Given this novel treatment, duration of action in our study is unknown.
- Expected side effects include:
  - Weakness in the muscle injected
  - Injection site pain
  - Injection site bleeding

### **6.5 Starting Dose and Dose Escalation Schedule**

None

### **6.6 Dose Adjustments/Modifications/Delays**

Following injection, dosage cannot be changed and study will maintain the aforementioned dose for the duration of this study. Based on studies for other indications, Botox has been shown to take effect in approximately 2 weeks and last between 2 and 4 months.

### **6.7 Prior and Concomitant Therapy/ Standard of Care**

Patient will not undergo concomitant medical therapy including, but not limited to physical therapy or surgical fasciotomy. If the patient has undergone previous physical therapy for the same diagnosis, this data will be collected but will not alter ability to participate in the study. Allowed in the study are over-the-counter pain medications including NSAIDs and Tylenol as needed.

### **6.8 Randomization and Blinding of Study Drug**

The subjects and drug will not be blinded in this study and subjects will not be randomized into differing treatment arms.

### **6.9 Receiving, Storage, Dispensing and Return or Disposal of Study Agent**

**Table 2:** Study Agent information at a glance:

Name	Source	Storage	Dispensing	Disposal
Botox	UW Pharmacy	Stored in Pain Clinic refrigerator until time of injection	One-time injection will be performed by treating physician	Excess medication will be disposed of in appropriate medical waste containers

#### 6.9.1 Receipt of Drug Supplies

After reconstitution, study team will collect the medication from the UW Pharmaceutical Research Center and deliver the medication to the UW Clinic at The American Center. The designated study staff will count and verify that the shipment contains all the items noted in the shipment inventory. Any damaged or unusable study drug in a given shipment (active drug or comparator) will be documented in the study files.

#### 6.9.2 Storage

Drug will be stored in a cooled container during transport and stored at the UW Clinic at The American Center refrigerator set between 2° and 8° C until the time of injection.

#### 6.9.3 Dispensing

Drug will be ordered by the lead investigator prior to the scheduled clinic visit one. The drug will be prepared, assigned to the appropriate patient, and delivered to the UW Clinic at The American Center by the UW Pharmacy within 24 hours of the appointment. Regular study drug reconciliation will be performed to document drug assigned, drug consumed, and drug remaining. This reconciliation will be logged on the drug reconciliation form, and signed and dated by the study team.

#### 6.9.4 Return or Disposal

At the completion of the study, there will be a final reconciliation of drug shipped, drug consumed, and drug remaining. This reconciliation will be logged on the drug reconciliation form, signed and dated. Any discrepancies noted will be investigated, resolved, and documented prior to destruction of unused study drug. Drug destroyed on site will be documented in the study files.

### 7 Study Procedures

Procedure: Botox injection

Under ultrasound guidance, the affected muscle group will be identified. After placing ultrasound transducer gel over the area, a 10-mHz linear ultrasound probe will then be utilized to localize the specific, respective muscles within the compartment being analyzed in both short and long axis. After cleansing the skin with chlorhexidine solution and utilizing semi-sterile technique, the muscle will be injected proximally and distally with the respective amount Botox mixed to 100 unit: 1 mL. Ultrasound-guidance will be utilized to guide the needle placements into the mid-depth of the respective muscle utilizing long-axis view with injections being performed with in-plane technique. The area will be scanned to ensure avoidance of neurovascular structures. Following injection, the sites will be monitored for cessation of bleeding and any immediate side effects prior to discharge from the clinic.

Identification of muscles by landmarkxx:

- Gastrocnemius medial head
  - Located within the most prominent portion of the muscle belly located 1/4 the distance from the popliteal crease to the Achilles insertion. Subject with plantarflex their foot against slight resistance allowing palpation of the muscle belly which becomes tendon about 1/2 way down the lower leg. Muscle belly will be identified on ultrasound with depth appropriate to delineate the soleus from the gastrocnemius.

- Gastrocnemius lateral head
  - Located within the most prominent portion of the muscle belly located 1/3 the distance from the fibular head to the achilles insertion. Subject with plantarflex their foot against slight resistance allowing palpation of the muscle belly which becomes tendon about ½ way down the lower leg. Muscle belly will be identified on ultrasound with depth appropriate to delineate the soleus from the gastrocnemius.
- Fibularis longus / Lateral compartment
  - Located ¼ of the distance from the fibular head to the tip of the lateral malleolus. Subject can laterally flex their foot against slight resistance to accentuate the muscle belly which becomes tendon ½ way down the lower leg.
- Tibialis anterior
  - Located 1/3 the way between the fibular head and the tip of the medial malleolus directly lateral to the anterior border of the tibia. Subject can dorsiflex their ankle against slight resistance to accentuate the muscle belly.
- Tibialis posterior
  - Medial approach is midway between heel and popliteal crease, which will avoid nerves and vessels. Injection depth is just posterior to the tibia after passing through the gastrocnemius and soleus.

## 7.1 LABS

There are no labs that are anticipated to be drawn in this study.

## 7.2 Established Standard of Care:

**Table 3.** Study Calendar

Process	Screening	Baseline (initial clinic visit; time 0)	Follow-up 1 (2 months, in clinic)	Follow-up 2 (4 months, telephone)	Final Visit (6 months, telephone)
IMP Measurement	SOC	X			
UWRI		X	X	X	X
Kio Force Measurement		X	X		
Botox injection into TA		X			

Indicate if study or standard of care by using "X" for study and "SOC" for standard of care.

## 7.3 Study Visits

### 7.4.1 Screening/Baseline:

Screening and consent will be discussed with PI at clinic visit in which IMP measurement (CECS diagnosis) is taken prior to enrollment in the study. If patient is not from local community, study will be discussed over telephone prior to enrollment. Once consent is obtained, baseline force measurements and UWRI (at study clinic visit 1) will both be scheduled within 1 month of IMP measurement.

### 7.4.2 Follow up:

**Table 4.** Acceptable Window for Study Visits (including weekends)

Visit	Window	Activities
-------	--------	------------

Study visit 1 (establishes time 0 of study)	Within 1 months of IMP measurement	
 
Written consent reviewed and collected
 
UWRI baseline
 
Kiio Force measurement
 
Botox injection
 

Follow-up 1 (Clinic)	2 months +/- 5 days	
 
UWRI
 
Kiio Force measurement of
 
Evaluation for side effects
 

Follow-up 2 (Telephone)	4 months +/- 1 week	
 
UWRI
 
Evaluation for side effects
 

Follow-up 3 (Telephone)	6 months +/- 1 week	
 
UWRI
 
Evaluation for side effects
 

#### 7.4.3 Unscheduled:

Possible AEs: Following investigators learning of potential AEs, subject will be contacted over telephone to discuss case. If deemed warranted by the investigator's clinical impression, subject will be scheduled for evaluation in clinic at earliest available appointment. Subject will be evaluated by investigator and symptoms addressed as clinically appropriate. If symptoms deemed a side effect of the medication, these will be documented in the patient's chart for inclusion in the medication effects.

#### 7.4.4 Final Study Visit

Study will conclude for each subject after the 6-month telephone follow-up encounter as each subject will only undergo a single injection for the study and will not be evaluated again under this protocol. Given the medication duration of action, adverse effects should not occur following this encounter. However, participants will be permitted to contact the study investigators should possible AEs occur, at which point the protocol mentioned above in 7.4.3 will be followed.

### 8 Study Analysis

#### 8.1 Sample Size Determination

Using a one-way ANOVA and assuming independence of leg scores for each patient, we will have 80% power to detect an overall significant F-test (assuming a 2 (SD=1) point decrease in pain score from baseline to 6 months) with n=6 patients (e.g. 12 legs). Accounting for potential drop-out (15%) and, additionally, adjusting for non-parametric analyses, **n=10 patients (e.g 20 legs) will be sufficient** to provide preliminary effect sizes at each time point which will help inform power analyses for studies planned beyond this pilot study.

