### Study Summary

## ONABOTULINUMTOXINA (BOTOX) EFFECT ON PAIN AND FUNCTION IN RECURRENT CHRONIC EXERTIONAL COMPARTMENT SYNDROME: A PILOT STUDY

Title	OnabotulinumtoxinA (Botox) effect on pain and function in recurrent chronic exertional compartment syndrome: a pilot study
Short Title and Precis	Botox for the treatment of recurrent chronic exertional compartment syndrome
Methodology	Open label pilot study
Study Duration	2 years
Study Center(s)	University of Wisconsin Hospitals and Clinics
Objectives	Determine effect of Botox on pain and function using the University of Wisconsin Running Index
Number of Subjects	10 subjects consisting of 20 legs
Diagnosis	Recurrent chronic exertional compartment syndrome (R-CECS)
Main Inclusion Criteria	Patients greater than 18 years of age with diagnosis of R-CECS
Main Exclusion Criteria	Diagnosis other than CECS
Study Product, Dose, Route, Regimen	Botox (reconstituted at 100 units/mL) to be injected under standard palpatory technique into the affected lower leg compartment. Dosage will be based upon the affected muscles
FDA status of product	FDA approved
Duration of administration	6 month follow up time after injection of medication. Typical duration of action of Botox is 10-12 weeks
Reference therapy	No direct comparison
Statistical Methodology	Using a one-way ANOVA and assuming independence of leg scores for each patient, we will have 80% power to detect an overall significant F-test (assuming a 2 (SD=1) point decrease in pain score from baseline to 6 months) with n=6 patients (e.g. 12 legs). Accounting for potential drop-out (15%) and, additionally, adjusting for non-parametric analyses, n=10 patients (e.g 20 legs) will be sufficient to provide preliminary effect sizes at each time point which will help inform power analyses for studies planned beyond this pilot study.

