#### 8.2 Statistical Methods

Basic descriptive statistics, means (SD) and medians (IQR) for continuous variables and frequencies (percentages) for categorical variables will be used to summarize patient outcomes. For the primary outcome, change in pain (from baseline on 0-10 numeric rating scale) will be assessed at each time point (2,4,6 months) using Friedman's ANOVA. Friedman's ANOVA is the non-parametric analog to one-way repeated measures ANOVA and is often

used for ordinal outcomes. If necessary and feasible, GEE models will be constructed to further assess changes in pain while accounting for intra-subject correlation. Secondary endpoints utilizing the UWRI will also be assessed in this manner. Change in strength outcomes at baseline and 2 months will be assessed using Wilcoxon signed rank tests or, if necessary, linear mixed effects models for repeated measures, to account for intra-subject correlation (left and right legs).

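### Does Section 8.1 need correcting because its 80% power for 6 patients (12 legs) cannot be traced to one calculation?

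*Combined protocol and SAP*

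**What the plan says.** Section 8.1, repeated in the Statistical Methodology row of the Study Summary, bases its calculation on a one-way ANOVA, "assuming independence of leg scores for each patient". It states "we will have 80% power to detect an overall significant F-test (assuming a 2 (SD=1) point decrease in pain score" between baseline and 6 months, "with n=6 patients (e.g. 12 legs"). It then raises 6 patients to 10, for 15% drop-out and for the use of non-parametric methods, and calls 10 patients sufficient to give preliminary effect sizes for planning later studies. The Study Summary lists "10 subjects consisting of 20 legs".

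Section 8.2 describes the primary analysis: "change in pain (from baseline on 0-10 numeric rating scale) will be assessed at each time point (2,4,6 months"), by Friedman's ANOVA. GEE models that allow for intra-subject correlation in pain follow if necessary and feasible. For strength, the plan names mixed models, if necessary, "to account for intra-subject correlation (left and right legs").

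On the time course, Section 6.6 says that for other indications "Botox has been shown to take effect in approximately 2 weeks and last between 2 and 4 months", and Section 6.4 says "Given this novel treatment, duration of action in our study is unknown".

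**The concern.** A power statement should let a reader recompute it, and this one leaves out five inputs. Read plainly, a fall measured from baseline makes baseline one of the ANOVA levels. With 12 independent legs and a score SD of 1, power is then far above 80% whatever the means at 2 and 4 months. If instead only the three change scores in Section 8.2 are compared, 80% can be recovered. That F-test, however, compares the follow-up visits with each other and has no power against a benefit that is the same at every visit.

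The two readings differ in unit, SD, hypothesis and reliance on leg independence. If the 80% belonged to the wrong contrast or the wrong unit, the trial might be too small for its purpose, or a later study might reuse a figure whose meaning is unknown. A linear fall to 6 months would also sit oddly with an effect that starts within weeks and wears off after 2 to 4 months.

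**Working it through.** **Inputs.** From Section 8.1: fall of 2 points, SD 1, 6 patients or 12 legs, stated power 80%. From Section 8.2: follow-up at 2, 4 and 6 months. Assumed, because not stated: alpha 0.05 and the means at 2 and 4 months.

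**Formula.** For k levels with n observations each, λ = n·Σ(μⱼ − μ̄)²/SD². Power = P(F′ > F_crit), where F′ is noncentral F with k − 1 and k(n − 1) degrees of freedom and noncentrality λ. Means below are written as points of fall.

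**1. Reproducing 80% with n = 6 (baseline a level, k = 4, score SD 1).** A linear fall has means 0, 0.67, 1.33, 2.
- Σ(μⱼ − μ̄)² = 1 + 0.111 + 0.111 + 1 = 2.222
- λ = 6 × 2.222 = 13.33; df 3 and 20; F_crit = 3.10
- Power = **80.2%**, and 6 is the smallest n that reaches 80%.

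**2. Reproducing 80% with n = 12 (three change scores, k = 3, SD of change 1).** A linear fall has means 0.67, 1.33, 2.
- Σ(μⱼ − μ̄)² = 0.444 + 0 + 0.444 = 0.889
- λ = 12 × 0.889 = 10.67; df 2 and 33; F_crit = 3.28
- Power = **80.4%**, and 12 is the smallest n that reaches 80% (n = 11 gives 76.2%).

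**3. The reading that does not give 80% (k = 4, n = 12, score SD 1).** The least favourable means are 0, 1, 1, 2.
- Σ(μⱼ − μ̄)² = 1 + 0 + 0 + 1 = 2; λ = 24; df 3 and 44
- Power = **98.48%**. A linear fall gives 99.2%. Even at alpha 0.01 the minimum is 93.0%.

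**4. Does 80% require a linear fall?** No.

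| Calculation | Falls at the visits | Power |
|---|---|---|
| k = 4, n = 6 | 0, 1.5, 1.5, 2 | 80.7% |
| k = 4, n = 6 | 0, 1, 1.5, 2 | 79.5% |
| k = 3, n = 12 | 0.85, 0.85, 2 | 80.1% |
| k = 3, n = 12 | 0.85, 2, 2 | 80.1% |

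The first row is an early-onset course. The stated power therefore does not commit the plan to a gradual fall, and nothing in Sections 6.4 or 6.6 contradicts it: one describes other indications and the other says that the duration here is unknown.

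**5. How far the figure moves with the unstated means.** For k = 4, n = 6, power is 75.5% for 0, 1, 1, 2 and 97.3% for 0, 0, 2, 2. For k = 3, n = 12, it is 67.5% for 1, 2, 2 and 5% for 2, 2, 2. With a linear fall and both legs of each patient fully correlated, the k = 3 test has in effect n = 6 and power 44.8%.

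**6. Is the trial too small for the 2-point fall?** Paired t-test, SD of change 1, n = 6: noncentrality = 2 × √6 = 4.90 on 5 df, power **97.1%**. With n = 12 it exceeds 99.9%. The 6 units here can be whole patients, so this result does not need independent legs.

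**7. From 6 to 10 patients.** 6/0.85 = 7.06, so 8 patients cover drop-out, and 10 leaves two more for the non-parametric analysis.

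**The case for a change.** The strongest case for a change is that matching the figure in two incompatible ways is not the same as verifying it. If step 1 was the calculation, the reference to 12 legs and the independence clause play no part in it. If step 2 was, the 80% is not power for the fall from baseline that the sentence describes, and it relies on independent legs. The plan does not say which was run, the pilot is meant to feed later power analyses, and the repair is one sentence in two places.

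The facts in this stand: Section 8.1 is under-specified, and the three-visit F-test is not a test of the fall from baseline. The consequence does not follow, for three reasons.

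- No corrected figure can be named. The remedy is to look up the calculation and write it down, and that leaves the sample size, endpoint and analysis as they are.
- Later studies would be planned from the effect sizes and SDs observed here, not from this planning sentence.
- The low values are extremes. 5% needs an identical mean fall at every visit. 44.8% needs perfectly correlated legs, and it stops at 6 patients when 10 are planned. The independence assumption is declared openly, and Section 8.2 provides GEE for intra-subject correlation in pain as well as mixed models for strength.

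**Conclusion.** No change to the plan. The 80% is poorly described but not shown to be wrong: it reproduces at 6 units with baseline as a level (80.2%) and at 12 legs with three change scores (80.4%). Only the combination of baseline as a level, 12 independent legs and score SD 1 contradicts it (at least 98.4%), and on that reading the stated figure is conservative. These results assume alpha 0.05 and SD 1, and the two matches also need particular visit means, of which a linear fall is one example among several.

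Ten patients are not shown to be too few. The plan justifies that number by preliminary effect sizes, and a paired test of the 2-point fall has 97.1% power with 6 units if the SD of change is 1. What remains is missing reporting detail, which the study statistician can supply from the calculation that was run.

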#### 8.2 Statistical Methods

Basic descriptive statistics, means (SD) and medians (IQR) for continuous variables and frequencies (percentages) for categorical variables will be used to summarize patient outcomes. For the primary outcome, change in pain (from baseline on 0-10 numeric rating scale) will be assessed at each time point (2,4,6 months) using Friedman's ANOVA. Friedman's ANOVA is the non-parametric analog to one-way repeated measures ANOVA and is often

used for ordinal outcomes. If necessary and feasible, GEE models will be constructed to further assess changes in pain while accounting for intra-subject correlation. Secondary endpoints utilizing the UWRI will also be assessed in this manner. Change in strength outcomes at baseline and 2 months will be assessed using Wilcoxon signed rank tests or, if necessary, linear mixed effects models for repeated measures, to account for intra-subject correlation (left and right legs).

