Recently, it has been hypothesized that botulinum toxin could reduce intramuscular pressure in CECSxv. Isner-Horoboti et alxv, performed abobotulinum toxin A injections into the anterior and anterior/lateral compartments in 16 individuals with a mean follow up of 4.4 months (range 3-6 months). Fifteen (95%) patients were asymptomatic after intervention with fourteen (88%) exhibiting normalized postexercise compartment pressures. Using manual muscle testing, they determined that 11 patients displayed decreased strength though did not produce noticeable subjective weakness. A later case report by Baria and Sellonxvi presented the first long-term follow up (14 months) of a CECS case treated with botulinum toxin injections (Botox) in which the patient reported continued pain relief and had resumed her active lifestyle without adverse effects. Finally, Hutto et alxvii demonstrated 11 months of pain relief following botulinumtoxin injection in a military recruit for CECS.

The proposed investigation will aim to build upon the results of existing studies. The novelty of our approach involves a differing dosage of the toxin (Botox) into a more targeted muscle group. Further, while previous studies have used manual muscle testing to test strength, many studies have found this method unreliable. As such, we will be using the Kiiro force sensor at multiple time points to determine weakness quantitatively. We will be utilizing the reliable and validated University of Wisconsin Running Index to evaluate return to sport. Finally, and most importantly, we will be treating a group of patients (R-CECS) for whom no current treatment is available. To date, there are no published articles on using Botox to treat R-CECS although, in clinic, the PI has treated an individual with great success utilizing this approach.

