## 2.2 Hypothesis

Hypothesis: Injection of Botox into the affected muscle group will alleviate pain associated with R-CECS.

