#### 4.1.1 Primary Study Endpoints

1. Decrease in pain by 2 points on 0-10 numeric rating scale with activity, measured in each leg

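### The primary Friedman test, as written, compares the follow-up visits with each other and not with baseline, so it cannot show a sustained fall in pain

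*Combined protocol and SAP*

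**What the plan says.** Section 8.2 (Statistical Methods) sets the main pain analysis as follows: "change in pain (from baseline on 0-10 numeric rating scale) will be assessed at each time point (2,4,6 months) using Friedman's ANOVA". The variable is change, the listed levels are the three follow-up visits, and baseline enters only by subtraction. The UWRI endpoints follow the same route: "Secondary endpoints utilizing the UWRI will also be assessed in this manner". GEE models are planned only where needed and workable, and no contrast is given for them. A paired test against baseline (Wilcoxon signed rank) is named in 8.2 for strength only.

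The rest of the protocol asks about a fall from baseline:

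- Section 2.2, hypothesis: "Injection of Botox into the affected muscle group will alleviate pain associated with R-CECS".
- Section 4.1.1, primary endpoint: "Decrease in pain by 2 points on 0-10 numeric rating scale with activity, measured in each leg".
- Section 8.1, sizing: "assuming a 2 (SD=1) point decrease in pain score from baseline to 6 months". The same section says that the pilot is "to provide preliminary effect sizes at each time point".

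**The concern.** The null hypothesis of the written test is that pain is alike at 2, 4 and 6 months. Early relief that lasts, which would be a clear success under section 2.2, fits that null exactly. A significant result, on the other hand, may mean only that relief wore off, or that pain got worse between visits. The primary p-value therefore does not bear on whether pain fell.

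Sustained relief is a realistic pattern on the protocol's own account. Section 6.6 says that for other indications "Botox has been shown to take effect in approximately 2 weeks and last between 2 and 4 months", so onset comes before the first follow-up at 2 months. Section 2.1 cites a report that "demonstrated 11 months of pain relief following botulinumtoxin injection in a military recruit for CECS" and another case with relief at 14 months. The 2-4 month duration in 6.6 makes fading possible as well; in that case the test would detect the fading and not the relief.

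**Working it through.** **1. The plan's own 80%.** Inputs from 8.1: one-way ANOVA, 2-point fall, SD 1, 6 patients (12 legs), legs independent. Alpha is not stated; 0.05 is assumed. Power comes from the noncentral F distribution with λ = n·Σ(μⱼ − μ̄)²/σ².

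- Baseline included, linear fall (0, −2/3, −4/3, −2), 6 per visit: Σ = 20/9, λ = 6 × 2.222 = 13.33, df 3 and 20, power 0.802.
- Follow-up visits only (−2/3, −4/3, −2), 6 per visit: Σ = 8/9, λ = 5.33, df 2 and 15, power 0.448.
- Follow-up visits only, same means, 12 legs per visit: λ = 10.67, df 2 and 33, power 0.804.
- Sustained fall, 6 per visit: with baseline (0, −2, −2, −2) power is 0.912. With follow-up visits only (−2, −2, −2), λ = 0 and power equals alpha, 0.05.

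The 80% can thus be reached with baseline in the model (6 per visit) or without it (12 legs per visit and a gradual fall). It does not settle which test was meant. It does show that, without baseline, a sustained fall contributes nothing.

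**2. Why subtracting baseline does not help.** For leg i, let dᵢⱼ = yᵢⱼ − yᵢ₀. Then dᵢⱼ < dᵢₖ exactly when yᵢⱼ < yᵢₖ, and ties stay ties. Friedman's statistic uses only within-leg ranks, so the test on three changes is the test on the three raw follow-up scores with baseline deleted. This needs no assumption. In simulation the two p-values agreed in 30,000 of 30,000 data sets.

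**3. An extreme case.** Ten blocks each fall from 7 to 3 and stay there. As written, all three changes are −4, everything is tied, and p = 1. With baseline included, the ranks in each block are 4, 2, 2, 2 and the rank sums are 40, 20, 20, 20. With k = 4, C = nk(k+1)²/4 = 250 and A = Σ(rank²) = 10 × 28 = 280:

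Q = (k−1)(ΣRⱼ² − nC)/(A − C) = 3 × (2800 − 2500)/30 = 30, df 3, p = 1.4 × 10⁻⁶.

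**4. Rejection rates.** 10 patients, 20 legs, four visits, scores rounded to 0-10, 1,500 trials per cell. Assumed, not in the protocol: baseline mean 7, SD of a single score 1 or 2, correlation 0.5 between visits in a leg, correlation 0 or 0.5 between legs. Independent legs, as 8.1 assumes:

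| True pattern | Test | SD 1 | SD 2 |
|---|---|---|---|
| No change | Friedman as written | 0.049 | 0.049 |
| Sustained 2-point fall | Friedman as written | 0.041 | 0.048 |
| Sustained 4-point fall | Friedman as written | 0.041 | 0.040 |
| Relief of 3, 2, 1 points | Friedman as written | 1.000 | 0.931 |
| Sustained 2-point fall | Friedman, four visits | 1.000 | 0.981 |
| Sustained 2-point fall | Signed rank vs baseline, patient level | 1.000 each visit | 0.961-0.969 |

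The patterns 2, 2, 2 and 3, 2, 1 have the same average relief, (3 + 2 + 1)/3 = 2, and get opposite answers. Repeat runs put the written test at up to 5.7% for the sustained 2-point fall. They also gave 92-100% rejection when pain was unchanged at 2 months and then worsened by 1 and 2 points.

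With leg correlation 0.5, the written test rejects in 0.106 (SD 1) and 0.118 (SD 2) of trials, both with no change and with a sustained 2-point fall. The rate is inflated by treating legs as independent, but there is still no power for the fall.

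**The case against.** The strongest reply is that the authors meant Friedman across four visits. Section 8.2 describes it as the rank version of repeated-measures ANOVA, 8.1 sizes the study on a fall from baseline, and the three months listed may say when change is assessed and not which levels enter the test. That may be so, and the four-visit test does detect sustained relief. The text does not say it, however, and the 80% figure fits either reading. A four-visit omnibus test is also non-directional and gives no comparison with baseline at each visit.

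Second, this is an open-label, single-arm pilot of 10 patients meant to supply effect sizes, and no decision rule hangs on the p-value. The planned means and medians would show the fall. This stands, and it confines the fault to the primary and UWRI tests. The protocol nevertheless states an efficacy objective, names a primary test and claims power for an F-test.

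Third, section 8.3 turns to GEE or linear models if patients drop out. At 15% drop-out the chance of at least one among 10 is 1 − 0.85¹⁰ = 0.80, assuming independence, so a model may well be fitted. Neither 8.2 nor 8.3 states a contrast with baseline for it.

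Fourth, the 2-4 months in 6.6 and the 10-12 weeks in the Study Summary suggest that relief may fade by 6 months, where the written test does reject. A rejection of that kind shows change during follow-up, not a fall from baseline.

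**Conclusion.** The concern holds for section 8.2 as written and must be fixed. For a sustained fall the primary test has no power beyond its false-positive rate (about 4-6% with independent legs, whether the fall is 0, 2 or 4 points), while relief that fades gives 93-100%. The rank argument is exact; the rejection rates rest on the assumed alpha, baseline mean, SDs and correlations. The same fault carries over to the UWRI endpoints tested in this way. The descriptive summaries are unaffected. If four visits were intended, the lack of power disappears, but the plan still has no test against baseline at each time point.

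**What to change.** In section 8.2, replace Friedman on change scores with prespecified comparisons of 2, 4 and 6 months against baseline, using one of:

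- the Wilcoxon signed-rank test, already named there for strength, on each patient's average over legs; or
- a GEE or mixed model on leg scores, with visit as a factor that includes baseline and patient as the cluster.

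Report an estimate with a 95% confidence interval at each visit. Name one visit as primary, or state a multiplicity rule over the three (Holm, for example). Apply the same to the UWRI endpoints. If Friedman is kept as supportive, state that it uses all four raw scores (0, 2, 4 and 6 months).

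**Cost.** Only analysis wording changes, because 8.2 already needs pain scores at all four visits. Tables 3 and 4 do not list the pain score separately, so the sponsor should confirm that it is recorded at each visit. The omnibus p-value is no longer the headline. Holm costs little at SD 1: power per visit for a 2-point fall is at least 99.9%. At SD 2 with leg correlation 0.5 it is 76-77% with the exact test, against 87-89% unadjusted with the normal approximation. Averaging legs makes the patient the unit; the clustered model keeps the leg but needs a small-sample correction with 10 patients.
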